### 8.5 Protocol Deviations

Protocol Deviations will be summarized by major and minor categories for the PPS, FAS and SAF. All Protocol Deviation data will be listed.

#### 8.5.1 Major Protocol Deviations

Protocol deviations are defined as any departure from the procedures defined in the protocol. Major deviations will include, but are not limited to the categories outlined in [Table 12](#):

#### **Table 12 Major Protocol Deviations with Impact on Evaluability**

##### **Confidentiality Statement**

---

Data and information contained in this document are considered to constitute trade secrets and confidential commercial information, and the legal protections provided to such trade secrets and confidential information are hereby claimed under the provisions of applicable law. No part of this document may be publicly disclosed without the written consent of Philip Morris Products S.A.

---

Category	Description
Any violation of inclusion/exclusion criteria	Considered a major deviation. The blinded data review team will decide on whether it impacts evaluability.
Mis-randomization (wrong information provided to randomization system)	Considered a major deviation with impact on evaluability.  Mis-randomized subjects will be classified according to their actual exposure arm for safety analysis.
Use of any nicotine or tobacco-containing product other than the assigned product during the exposure period	Considered a major deviation. The blinded data review team will decide on whether it impacts evaluability.
Assessments related to the primary objective performed outside the time tolerance (see Table 13 )	Considered a major deviation. The blinded data review team will decide on whether it impacts evaluability.

### 8.5.2 Minor Protocol Deviations

Minor deviations may include, but are not limited to, use of concomitant medication and assessments performed outside the time tolerance (see [Table 13](#)).

### 8.5.3 Assessment Time Points and Assessment Time Windows

[Table 13](#) contains the list of assessments that have a time constraint and an acceptable tolerance.

**Table 13 Assessment Time Constraints and Time Windows**

Related to Primary Objective	Assessment	Time constraint	Tolerance

#### Confidentiality Statement

Data and information contained in this document are considered to constitute trade secrets and confidential commercial information, and the legal protections provided to such trade secrets and confidential information are hereby claimed under the provisions of applicable law. No part of this document may be publicly disclosed without the written consent of Philip Morris Products S.A.

Yes	Blood sample at days -1 and 6 or during early termination visit	After $\geq$ 6 hours of fasting	Not applicable
No	CYP1A2 activity at days -1 and 5	Collection of blood sample 6 hours after intake of caffeine tablet	+/- 15 minutes
Yes	24-hours urine	24h	+/- 1 hour

## 9 PLANNED STATISTICAL METHODS

### 9.1 General Considerations

The statistical evaluation will be performed using SAS®, version 9.4 or later.

#### 9.1.1 Stratified Presentation

Sex (male and female) is used as a stratification factor during randomization and for the presentation of descriptive statistics. Race will also be used as stratification factor for the presentation of the descriptive statistics.

#### 9.1.2 Sub-group Analyses

No further sub-group analyses are planned.

#### 9.1.3 Descriptive Statistics

All data will be presented in listings, ordered by randomization arm, subject, and study day unless otherwise specified.

For continuous data, summary statistics will include the number of subjects (n), the number and percent of subjects with missing data, the arithmetic mean, arithmetic standard deviation (SD), 95% confidence interval (CI) of the arithmetic mean, median, first and third quartiles, minimum, maximum; for log-normal data, the geometric mean, geometric coefficient of variation (CV), and 95% CI of the geometric mean will be presented in addition.

#### Confidentiality Statement

Data and information contained in this document are considered to constitute trade secrets and confidential commercial information, and the legal protections provided to such trade secrets and confidential information are hereby claimed under the provisions of applicable law. No part of this document may be publicly disclosed without the written consent of Philip Morris Products S.A

Post-baseline summaries will include change from baseline apart from log-normal variables which will percentage change from baseline.

When applicable, the number and percentage of subjects with values below the lower limit of quantification (LLOQ) or above the upper limit of quantification (ULOQ) will also be presented.

For categorical variables frequency counts (n) and percentages (%) will be presented. The number and percentage of subjects with missing data will also be presented.

If the total number of items/events is zero, any further breakdown into sub-categories will not be presented.

Unless specified otherwise the denominator for percentages will be the total number of subjects in each respective group except missing data.

#### 9.1.4 Definitions for Statistical Data Analysis

At the time of the present protocol, no new terms are defined.

#### 9.1.5 Handling of Dropouts or Missing Data

##### 9.1.5.1 Laboratory Parameters

Values outside detection limits will be substituted using the following rules (e.g., for BoExp parameters):

- Values below LLOQ will be imputed using LLOQ/2.
- Values above ULOQ will be imputed using ULOQ.

Unless otherwise stated, other missing values will not be imputed.

##### 9.1.5.2 Questionnaires

Missing data will be handled as follows for the ABOUT – Product Experience Questionnaire.

If there are more than or equal to 50% of within-person item-level missing data within a domain/scale, the missing item-levels will be kept as missing, and the domain/scale score will be set to missing. If there are less than 50% of within-person item-level missing data within a domain/scale, the following rule will be used to produce a complete within-person response pattern:

---

#### Confidentiality Statement

Data and information contained in this document are considered to constitute trade secrets and confidential commercial information, and the legal protections provided to such trade secrets and confidential information are hereby claimed under the provisions of applicable law. No part of this document may be publicly disclosed without the written consent of Philip Morris Products S.A.

---

1. Sum the available within-person item responses and divide that score by the number of items which have responses.
2. Replace the items with missing responses with the within-person mean.
3. Calculate a domain/scale score to two significant digits by using all items and the standard formula used when all items are not missing.

For the Fagerström Test for Nicotine Dependence Questionnaire, the total score is set to missing if any of the items is missing (see Appendix 13.2). No imputation of missing value will be done for the Nicotine/Tobacco Product Use History Questionnaire.

#### 9.1.5.3 Missing or Partial Dates

Dates missing or partial will not be imputed for AEs, medical history, and concomitant medications, but the following assumptions will be made to assign them to categories:

Date Information	AE Category	Disease Category	Medication Category
If the date is completely missing, or for partial dates, if the month/year is the same as, or later than the month and/or year of screening	NA	Concomitant Disease	Concomitant Medication
For partial dates, if the month/year is earlier than the month and/or year of screening	NA	Medical History	Prior Medication

#### 9.1.5.4 Insufficient Data for Analysis/Presentation

If there are no values or events for a planned output, the blank TFL shell will be presented with a message printed in the center of the table, such as, “No adverse events related to study procedures occurred for this study”.

For stratified analyses, strata with <5 subjects overall will not be presented.

#### 9.1.6 Handling of Unplanned Data

If any unplanned assessments do occur, they will be included in listings only. Only planned assessments will be summarized.

### 9.1.7 Multiple Comparison/Multiplicity

Overall family-wise type I error will be preserved at the  $\alpha$ -level of 2.5% (1-sided tests will be conducted for the primary and key secondary study hypotheses). This will be done by using a fixed sequence of testing: primary objective  $\rightarrow$  1st key secondary objective  $\rightarrow$  2nd key secondary objective  $\rightarrow$  3rd key secondary objective  $\rightarrow$  4th key secondary objective  $\rightarrow$  5th key secondary objective. All objectives will be tested sequentially in a given order at the 2.5% type I error level until one of the objectives is rejected in which case all subsequent testing will be exploratory 2-sided tests at an  $\alpha$ -level of 5%, and the associated 2-sided 95% confidence interval will be reported.

The primary study hypothesis will be tested 1-sided with a type I error  $\alpha$ -level of 2.5%. The associated 1-sided 97.5% confidence interval will be provided. This will be applied to all BoExps of [Table 1](#) that are part of the primary study hypothesis. Subsequent analyses of objectives will only proceed if this hypothesis is not rejected.

If the primary study hypothesis is not rejected, the same  $\alpha$ -level of 2.5% will be used for the 1st key secondary hypothesis and the associated 1-sided 97.5% confidence interval will be reported. This will be applied to all BoExps of [Table 2](#) that are part of the 1st key secondary hypothesis. Subsequent analyses will only proceed if the hypothesis is not rejected.

The analysis will proceed in a similar way for the following key secondary objectives.

For all the exploratory objectives, the statistical tests will be 2-sided with an  $\alpha$ -level of 5%. Associated 2-sided 95% confidence intervals will be provided.

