### Confidentiality Statement

Data and information contained in this document are considered to constitute trade secrets and confidential commercial information, and the legal protections provided to such trade secrets and confidential information are hereby claimed under the provisions of applicable law. No part of this document may be publicly disclosed without the written consent of Philip Morris Products S.A

LS-means per randomization arm and day will be obtained (on the log-scale), as well as pairwise differences between arms per day, together with their 95%-confidence intervals and (unadjusted) p-values. Exponentiation of these quantities will lead to the geometric LS-means per randomization arm and (geometric) ratios between arms with their associated 95%-confidence intervals.

The exponentiation of the 'lsmestimate' statement above entitled 'Contrast P4M3 (CA35 and CM35 combined) vs. CIG' will allow contrasting the two P4M3 Gen 2.0 CA35 and CM35 study arms combined against the CIG arm and will be used to assess the primary study hypotheses. Similarly, the exponentiation of the two subsequent 'lsmestimate' statements will be used to assess the key secondary objectives 2 and 4 if the procedure of fixed sequence testing allows it.

For each individual BoExp in the Primary Analysis, the hypothesis will be evaluated using the 1-sided statistical test with a type I error level of 2.5% given by the 'lsmestimate' statement 'Contrast P4M3 (CA35 and CM35 combined) vs. CIG' of the model described in this section.

The study will be declared successful if the ratio of the geometric means between P4M3 (CA35 and CM35 combined) over CIG is statistically lower than 1 at Day 5 for all four Primary BoExp.

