#### Confidentiality Statement

[figure not shown]
---

Data and information contained in this document are considered to constitute trade secrets and confidential commercial information, and the legal protections provided to such trade secrets and confidential information are hereby claimed under the provisions of applicable law. No part of this document may be publicly disclosed without the written consent of Philip Morris Products S.A.

---

if the primary objective is demonstrated, which preserves the study-wise type I error rate at the 2.5%. An additional benefit will be declared if the ratio of the geometric means between P4M3 (CA35 and CM35 combined) over CIG is statistically lower than 1 at day 5 for all four additional key secondary BoExp.

If both the primary and first key secondary objectives are successful, then the 2nd key secondary objective will be tested with type I error level of 2.5%, and similarly in sequence until objective 6 (Figure 2). If, during subsequent tests, any of the objectives are not successful, the sequence testing will stop, and further testing will cease. Specifically, if the hypothesis for a single BoExp is rejected, then the fixed sequence testing will stop.

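### SAP 9.1.7 misstates the fixed-sequence gate: testing continues when a hypothesis is not rejected, although the reduction has to be demonstrated

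*SAP*

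**What the plan says.** SAP 9.1.7 promises family-wise control at 2.5% with one-sided tests in a fixed order, and then words the gate by non-rejection:

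- After the primary: "Subsequent analyses of objectives will only proceed if this hypothesis is not rejected".
- For passing the level on: "If the primary study hypothesis is not rejected, the same" level applies to the first key secondary objective.
- After the first key secondary: "Subsequent analyses will only proceed if the hypothesis is not rejected".
- For the stop: testing runs "until one of the objectives is rejected in which case all subsequent testing will be exploratory".

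SAP 9.6.3.1 repeats the stop for individual biomarkers: "if the hypothesis for a single BoExp is rejected, then the fixed sequence testing will stop".

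The same section also states the rule the other way. The first key secondary is tested "if the primary objective is demonstrated, which preserves the study-wise type I error rate", and if "any of the objectives are not successful, the sequence testing will stop". SAP 9.6.1.2 defines primary success as a geometric mean ratio that "is statistically lower than 1 at Day 5 for all four Primary BoExp". SAP 3.2.1 and 3.5.2, protocol 12.6.1 and the gate sentences of protocol 12.9.3 agree: each objective must be demonstrated, with every BoExp significant.

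SAP 3.5.1 writes H1 to H6 as the reductions themselves (ratio below 1) and gives no null. SAP section 7, which lists changes from the protocol, mentions no change to the gate.

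**The concern.** A one-sided superiority test either rejects or fails to reject a null, here a ratio of 1 or more. Rejecting it is the success. A rule that continues on non-rejection and stops on rejection is therefore the reverse of a fixed-sequence procedure if the hypothesis meant is the null. If it is instead the reduction written in SAP 3.5.1, non-rejection means only that the data do not contradict a reduction, which is weaker than demonstrating one. Neither ordinary reading gives the rule that protects the 2.5%.

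The corresponding sentences of protocol 12.9.3 say demonstrated and not demonstrated, and add that all BoExp need to pass. SAP 9.1.7 changed the first and dropped the second. Five of the six confirmatory objectives depend on this gate, and 9.1.7 is where a programmer or assessor will look for it.

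**Working it through.** **Possible readings of 9.1.7**

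| Meaning given to *not rejected* | Effect of the gate |
|---|---|
| A. The null (ratio at or above 1) is not rejected | Reversed: primary success ends the sequence |
| B. The reduction claim is not significantly contradicted | Proceeds without demonstration |
| C. The objective is demonstrated | Intended rule; matches the other sections |

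**1. The plan's own power.** Inputs are the GMR and GCV values of protocol Tables 16 to 19 and the evaluable numbers in SAP section 6 (30 vs 15 combined, 15 vs 15 single variant). SD on the log scale = √ln(1 + GCV²); noncentrality = |ln GMR| / (SD·√(1/n₁ + 1/n₂)); one-sided 2.5% t-test.

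The least favourable source study is 1970982, at 30 vs 15, where √(1/30 + 1/15) = 0.3162 and the critical t on 43 df is 2.017:

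- 3-HPMA (52.86%, 39.57%): SD 0.3814, |ln GMR| 0.6375, noncentrality 0.6375/(0.3814 × 0.3162) = 5.29, probability of missing 0.00068.
- Total NNAL (49.03%, 42.51%): SD 0.4076, |ln GMR| 0.7127, noncentrality 5.53, probability of missing 0.00029.
- 2-CyEMA and COHb: negligible.

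The product of the four powers is 0.99904, so the stated power of at least 99% is reproduced. All six objectives together, multiplying as SAP section 6 does: 0.99904 × 0.99998 × 0.98908² × 0.99916² = 0.976 for this study. The other three give 0.9997 (1970995), 0.9976 (1989156) and 0.9932 (1959932). SAP Table 11 differs from protocol Table 19 in two entries for 1970982 (S-PMA GMR 45.68, total NNN GCV 57.69); with those the figure is 0.963. All are consistent with the SAP's at least 94% (0.99⁶ = 0.941).

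**2. Chance of reaching the first key secondary under reading A.** Testing continues only if the primary objective is not met:

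- 1970982: 1 − 0.99904 = 0.00096. The union bound, 0.00068 + 0.00029, gives the same to rounding, so correlation between BoExp does not matter.
- The other three studies: at most 0.0000032.
- With the literal single-BoExp stop of 9.6.3.1 added: effectively zero.
- Intended gate: at least 0.9990.

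A joint power of 94% cannot arise under reading A.

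**3. Family-wise error with one null BoExp per table.** Assume one BoExp of SAP Table 1 and one of Table 2 have GMR = 1 in both P4M3 arms, and the other six are so strongly reduced that they always pass. Arms CA35, CM35 and CIG have n = 15 each with CIG shared, and normal approximations are used (2,000,000 draws). Under A the sequence runs on until something is rejected, so the error is the probability that any of the six composites is falsely declared. The documents give no correlation between BoExp, so it is varied.

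| Assumed correlation | 0 | 0.3 | 0.5 | 0.7 | 0.9 | 1.0 |
|---|---|---|---|---|---|---|
| 9.1.7 alone, reading A | 9.4% | 9.0% | 8.6% | 7.9% | 6.7% | 4.8% |
| Intended gate | 2.5% | 2.5% | 2.5% | 2.5% | 2.5% | 2.5% |

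Reading B gives almost the same: 9.2% at correlation 0 and 6.7% at 0.9. If the literal 9.6.3.1 stop is applied together with reading A, the three reduced Table 1 biomarkers end testing at the first step, and the error returns to 2.5% at every correlation.

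**4. Family-wise error with all eight BoExp null** (400,000 draws, equal correlation). At correlations 0.5, 0.9 and 1.0, 9.1.7 alone gives 0.3%, 2.5% and 4.9%; both literal sentences together give 0.1%, 1.2% and 4.9%. The intended gate never exceeds 2.5%.

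**The case against.** The best defence is that the SAP defines the primary study hypothesis in 3.5.1 as the reduction, so a hypothesis that is not rejected is a reduction claim that stands, and the direction is right. Both documents also speak of an objective being rejected. An objective is not a null, so there the word can only mean failed, and making later tests exploratory makes sense only after a failure. The stop sentence in 9.6.3.1 directly follows a correct one and elaborates it. The correct rule appears in several other sections, and nobody planned the reversed procedure. The error rates above therefore describe a reading that the rest of the SAP excludes, under assumed correlations and an unfavourable configuration.

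Most of this stands. The intent is recoverable, reading A is plainly not intended, and the figures are not evidence that the planned analysis inflates alpha. What does not stand is that 9.1.7 is therefore right as written. On the SAP's own definition the gate becomes reading B, and failing to contradict a reduction is not demonstrating one. The intended rule needs a private meaning of *rejected* that the SAP never gives, and 9.6.3.1 uses the word that way in one sentence and states the rule correctly in its neighbours.

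**Conclusion.** The concern holds as a wording error in the confirmatory decision rule, and it should be corrected. SAP 9.1.7 and one sentence of 9.6.3.1 do not state the gate required by the protocol and the rest of the SAP. Taken literally against the null, the first key secondary would be tested with probability at most 0.00096 at the planning effects. Taken alone, 9.1.7 would not guarantee the 2.5% it promises. The first figure rests on the documents' planning values. The error rates rest on an assumed configuration and assumed correlations, and in the one-null-per-table case the excess disappears once the literal 9.6.3.1 stop is also applied. The intended fixed sequence, the sample size and the stated power are sound.

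**What to change.** In SAP 3.5.1, state the null for each BoExp and contrast: GMR at or above 1. In SAP 9.1.7, and in place of the single-BoExp sentence of 9.6.3.1, write the gate once, along these lines: *Proceed to the next objective only if the null is rejected at one-sided 2.5% for all four BoExp of the current objective (objective demonstrated); otherwise confirmatory testing stops and later objectives are exploratory (two-sided 5%).* The exploratory clause follows protocol 12.9.3. In the first paragraph of 9.1.7, let confirmatory testing run until an objective is not demonstrated.

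Protocol 12.9.3 uses *rejected* loosely in one sentence, which could be corrected at the same time if the protocol is amended; its gate sentences are already right. The necessary change is to SAP wording only, with no effect on design, data or programming.

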## 9.2 Disposition of Subjects

The number of subjects screened will be provided. The number and percentage (based on the number of subjects screened) of screen failures will also be provided, as well as the reasons for screen failures. The number and percentage (based on the number of subjects screened) of enrolled but not randomized subjects will also be reported.

Randomized subject disposition will be summarized by absolute counts (n) and percentages (%) and split by randomization arm and overall. Percentages will be based on the number of subjects in each randomization arm or overall. The number of subjects who completed the study, the number of subjects who prematurely discontinued, and the primary reason for withdrawal will be reported.

Disposition data will be listed.

---

### 9.3 Demographic and Other Baseline Characteristics

Demographics and baseline characteristics will be summarized as follows:

- By randomized study arm for the FAS
- By randomized study arm for the PPS
- By randomized study arm or a group of enrolled but not randomized subjects when applicable for the SAF

Demographic variables will include sex, age (years), race, body weight (kg), height (m), body mass index (BMI, kg/m^2). Body weight and BMI will be summarized at screening and admission. Baseline characteristics include TNP use history (average product use per day in the last four weeks, number of participants with continuous product use for the past 3 years, and other questions included in the Nicotine/Tobacco Product Use History questionnaire), spirometry measurements (FEV1, FEV1 % predicted, FVC, FVC % predicted, and FEV1/FVC), and FTND questionnaire score.

All demographic and baseline characteristics data will also be summarized using the stratification factors provided in section 9.1.1.

All demographic and baseline characteristics data will be listed.

### 9.4 Measurement of Product Compliance

The distribution and return of the P4M3 components (P4M3 Battery Unit and P4M3 Cartridge) will be documented in appropriate logs. CIG butts will be collected and documented for accountability. These data will be presented in listings.

